- 1. ≥18 years at admittance at participating hospital
- 2. Admittance in a department/Ward using systematised EWS
- 3. Admittance for more than 24 hours

Patients will be included at the first admission in the study period (index admission) and will remain in this group (intervention/control) for a follow-up period of 30 days. All subsequent admissions (readmissions) will be ignored.

Exclusion

- 1. Patients arriving at the gynaecological-, obstetric-, and paediatric department
- 2. If a "do not resuscitate"-order or "no NEWS/I-EWS registration" are identified, patients will be excluded for further analysis at the time of registration.

Definition of clusters

Eligible hospitals can consist of one or two units. A hospital is defined based on its administrative organisation and catchment area. Each hospital will generate one cluster and two (time) periods (control and intervention). See schematic figure 1 below

Randomisation

Prior to the study start participating clusters will be randomised to start as either intervention or control. Eight cluster will be available, and we will be using stratified randomisation based on size of hospitals (number of unique admissions, more than 25,000 admissions is defined as large hospitals, less than 25,000 is small hospitals), to balance a potential size difference between the intervention and control group. The randomization will be performed using computer-generated numbers. The randomisation will allocate participating hospitals to periods of intervention or control in a 1:1 ration. A cross-over will occur after 6.5 months and is expected to be at April 15, 2019.

Ethics

The study was presented to the Regional Ethics Committee, who decided that no formal approval was needed in accordance with Danish law (J.nr. 1701733). Data management has been approved by the Danish Data Protection Agency (ID: HGH-2017-116, I-suite:06030).

Study variables:

The following data are collected as a minimum for the included patients:

- Age and gender
- Personal Identification number (Danish Civil Registration number (CPR)

- Presence of Do Not Resuscitate (DNR) order
- Presence of "No EWS registration"
- EWS/I-EWS Scores
- Registered actions to the EWS/I-EWS escalation protocol
 - Responsible nurse contacted
 - Treatment plan already made
 - Doctor contacted
 - MET contacted
 - Other
 - Charlson Comorbidity Index

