The study is designed as a non-inferiority study to show that I-EWS is not inferior to the existing EWS algorithm with a non-inferiority margin (Δ) of 0.5% regarding 30-day all-cause mortality. The participating hospitals will admit 189,000 individual patients within one-year, individual sizes (admissions) are described on p.12. The sample size is based on the following assumptions: I) within a the inclusion period of ten months, the participating hospitals are expected to admit 150,000 individual patients II) mean all-cause mortality is 2.9% with variations as described on p. 11, III) a variation in mortality of 25% over the course of the year. The non-inferiority margin is set at 0.5%, and if the intervention has an effect of 0, the study has above 90% power to confirm noninferiority. In a previous cohort of 103,733 patients the mean (SD) number of scores per patient per day was 2.3 (2.0) and 15.4% of patients had one NEWS score of ≥ 6 . With the expected

inclusion, we will be able to detect a difference of 0.04 in mean number of scores and a difference of 0.6% in the number of patients with one NEWS \geq 6 with a power > 90%.

Study end

The follow-up for all patients ends after at total study period of 13 Months and is expected to end at the October 31, 2019.

Statistical plan for main outcome paper

Statistical analyses will be performed using SAS and R. Reporting of results will be in accordance with the CONSORT criteria with extension to cluster randomised trials. Analyses will be done using R. P < 0.05 will be considered statistically significant.

Consort diagram

A modified CONSORT trial profile will be used to describe patient flow and total number patients in each group and at each cluster. All patients not included in analysis will be explained.

Baseline description of groups:

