Table of summary statistics for patients and at hospital or cluster level for each group (intervention or control) will be presented with baseline variables (Number of patients, number of admissions, age, sex, Charlson Comorbidity index, hospital characteristics) Continuous variables will be summarized with: n (based on non-missing sample size), mean, standard deviation, median, interquartile range, number of missing values. Categorical variables will be reported as frequency and percentages (based on non-missing sample size) and number of missing values. Continuous and ordinal variables will be tested by Wilcoxon analysis or t-tests as appropriate for differences between groups. Categorical variables will be tested with chi-square.

Primary outcome analysis

The primary outcomes will be an **analysis of all-cause mortality and NEWS/I-EWS scores per patient per day between the intervention and control group**. Patients will be followed as one cohort and data will be analysed as randomized and in accordance with the intention-to-treat principle.

Inclusion: Patients will be included at the first admission at the participating hospitals in the study period (index admission) and will remain in this group (intervention/control) for follow-up of 30 days. Admission is defined as a contact to a hospital with a duration of more than 24 hours. All subsequent admissions (readmission) will be ignored. Any patient lost to follow-up will be censored at the last time known to be alive.

The main analysis of the primary outcome for motality will be done using logistic regression that accounts for clustering with adjustment for hospital ID, age, and sex. Intraclass correlation

coefficient with 95% confidence intervals will be reported. Results will be presented at the individual patient level. Assessment of cluster-level differences will be performed. NEWS/I-EWS scores per patient per day will be compared using linear regressions.

Each period will start with 14 days of implementation, and before cross-over patients will be followed by an observation period of 30 days Periods of implementation and observation will be censored in the analyses (patients admitted in these periods will not be included in the analyses). Cumulative incidence plots (1-survival) will be calculated using the Kaplan-Meier method and presented.

Sensitivity analyses of the primary endpoint

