In addition to the ITT analysis, a per-protocol analysis will be performed. In this analysis, interventional patients with missing or incomplete (missing a I-EWS modification in more than 1/3 of the total number of measurements) I-EWS measurement will be excluded. Finally, a sensitivity analysis will be performed, where patients that are transferred between hospitals will be excluded. Sensitivity analyses will be performed for the last three months of each intervention period and excluding departments where I-EWS protocol was not followed.

Subgroup analyses of primary endpoint

The primary outcomes will be calculated for the following subgroups, including a test for interactions: Age (\leq 39 years, 40 to 69 years, \geq 70 years), admissions at defined cluster, and according to the primary discharge diagnosis; cardiovascular disease, infections, pulmonary disease neurological disease, cancer and surgery done during admission. Results will be presented graphically using a forest plot.

Secondary endpoints

Secondary endpoints regarding mortality will be analysed using the same analysis as the primary endpoint. Length of hospital stay between groups will be compared by linear regression following the same adjustment principles as for the primary outcome.

Additional measurements

The frequency of changes in I-EWS that led to an escalation or de-escalation in the escalation protocol will be reported. Changes in NEWS due to CROS values and changes in I-EWS due to clinical assessment will be compared using Poisson regression models.

Handling of missing data

The primary outcome analysis should be subject to no or little missing data as it is based on Danish register data. Patients lost to follow-up (tourists) will be censored at the last registration.

Handling of diagnoses for outcome and subgroups

Diagnoses obtained from the National Patient Registry are coded with the ICD-10 system. The original chapters will be used to group patients according to diagnoses. The primary diagnosis will be used when constructing. The following will define the subgroups: **Cancer:** Chapter II: Neoplasms (C00-C97 + D37-D48). **Cardiovascular disease:** Chapter IX: Diseases of the circulatory system (I09-I52 + I70-I89)

Pulmonary disease: Chapter X: (DJ00-DJ99)

Infections: Chapter I: (A00-B99 + J00-J22 + N10-N11+ N30-N31 + G00-G09)

Neurological disease: Chapter VI: Diseases of the nervous system (G09-G47 + I60-I69)

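### The co-primary endpoint (scores per patient per day) is given only a linear regression with no clustering, hospital or period term, and its detectable difference of 0.04 states no design effect

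*SAP*

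**What the plan says.** The Endpoints section makes the number of scores per patient per day a co-primary endpoint, and the main hypothesis claims fewer of them with I-EWS. Three sentences on modelling need to be compared:

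- Mortality (Primary outcome analysis): "logistic regression that accounts for clustering with adjustment for hospital ID, age, and sex".
- Scores per patient per day (same paragraph): "NEWS/I-EWS scores per patient per day will be compared using linear regressions".
- Length of stay (Secondary endpoints): "Length of hospital stay between groups will be compared by linear regression following the same adjustment principles as for the primary outcome".

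The adjustment is therefore written for mortality and explicitly extended to a secondary endpoint, but not to the co-primary one. No model names a period term, although the design is a two-period cross-over.

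On precision, Sample size calculation says "we will be able to detect a difference of 0.04 in mean number of scores" with more than 90% power, from a mean of 2.3 and SD of 2.0. It gives no intraclass correlation (ICC) or design effect. The variation it does list, by hospital and over the year, concerns mortality.

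**The concern.** A regression that treats patients as independent has too small a standard error whenever a hospital's mean score frequency moves between periods for reasons other than the intervention. Leaving out period or hospital can also shift the estimate itself when hospitals differ in size or in their volumes per period.

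The SAP's own text gives reasons to expect period differences:

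- "A cross-over will occur after 6.5 months and is expected to be at April 15, 2019", so one period is mainly winter and the other mainly summer.
- Sample size calculation assumes "a variation in mortality of 25% over the course of the year", and the Introduction ties the interval to the next measurement to the score. Sicker patients are therefore measured more often.
- Only the index admission counts: "All subsequent admissions (readmissions) will be ignored". A patient already included in period 1 cannot enter period 2, which can change both the volume and the case mix of period 2.

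The claim of fewer scores per patient per day rests on this one model. If its standard error or estimate is wrong, that claim can be declared significant too easily.

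**Working it through.** **Inputs from the SAP.** 150,000 patients, taken as 75,000 per condition; SD 2.0; difference 0.04; alpha 0.05, taken as two-sided; 8 hospitals in 2 periods; hospital sizes from the table at the end.

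**Assumed, because the SAP gives no values.** The hospital-by-period SD *s*, the common period shift, the stable between-hospital SD, and the split of volume between periods.

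**1. The plan's own figure.** SE = 2.0 × √(2/75,000) = 0.01033.
- Normal power for 0.04 is Φ(0.04/0.01033 − 1.96) = 97.2%.
- The 90% detectable difference is (1.96 + 1.2816) × 0.01033 = 0.0335.

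So 0.04 with more than 90% power is right for independent patients. The companion figure in the same sentence, 0.6 points on 15.4%, has 90.1% power (against 14.8%) or 89.1% (against 16.0%) with a design effect of 1. That leaves no room for clustering. It suggests, but does not prove, that clustering was left out.

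**2. Type I error with the plain standard error.** True SE = √(0.01033² + 2s²Σw²), where w is each hospital's share of patients. Σw² = 1/8 for equal hospitals and 0.1537 for the table's sizes. Type I error = 2 × [1 − Φ(1.96 × 0.01033/SE)].

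| *s* (scores/day) | Equal sizes | Table sizes |
|---|---|---|
| 0.02 | 16% | 18% |
| 0.05 | 45% | 49% |
| 0.10 | 69% | 72% |

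**3. No period term, with *s* = 0.** The SAP states that "we will be using stratified randomisation based on size of hospitals". Four hospitals lie above 25,000 admissions and four below, so a 2:2 split in each stratum gives 6 × 6 = 36 allocations. The I-EWS share *p* of period 1 patients runs from 0.422 to 0.578. With equal period volumes, bias = shift × (1 − 2p).

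| Common period shift | Largest bias | Mean type I error over 36 allocations | Worst allocation |
|---|---|---|---|
| 0.1 | 0.0155 | 13% | 32% |
| 0.2 | 0.0311 | 32% | 85% |

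A hospital term alone does not remove this bias, so copying the mortality wording would not be enough.

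**4. No hospital term, with *s* = 0 and no period shift.** By simulation with the table's sizes and a stable hospital SD of 0.2, type I error is 5% when each hospital's two period volumes are equal, 12% at 52.5:47.5 and 28% at 55:45. With hospital and period terms, cases 3 and 4 return to about 5%.

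**5. Power for 0.04 with a small-sample reference.** Eight within-hospital period differences less two sequence means leave 6 degrees of freedom. The SE is as in step 2, with noncentral t.

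| *s* | Power, equal / table sizes | 90% detectable difference, equal / table sizes |
|---|---|---|
| 0 | 89.4% / 89.4% | 0.0404 / 0.0404 |
| 0.02 | 64% / 60% | 0.056 / 0.059 |
| 0.05 | 24% / 21% | 0.106 / 0.116 |
| 0.10 | 10% / 9% | 0.200 / 0.221 |

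On this reference the tolerable design effect is (0.04/0.0404)² = 0.98, so nothing is left for clustering.

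**The case against.** The strongest reply is that the SAP is silent here, not wrong. It introduces mortality and scores together as the primary outcomes. The ICC report and the assessment of cluster-level differences stand in the same paragraph, and reporting is to follow the CONSORT cluster extension. A sympathetic reader could take the clustering to cover both outcomes. But none of these commitments fixes a model or standard error for scores, the clustering sentence is confined to mortality, and the extension to length of stay shows that carry-over was written where it was meant. The ambiguity remains, and on either reading there is no period term.

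Some objections to the size of the problem do stand:

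- The exhausted power depends on the t reference with 6 degrees of freedom, which the SAP does not specify. On the normal reference power is 97.2%, and a design effect up to (0.04/0.0335)² ≈ 1.43 is tolerable. With no hospital-by-period variation, 89.4% is barely short of 90%.
- The SAP presents 0.04 as what the expected inclusion can detect, not as the smallest worthwhile difference. Larger effects are safer: at *s* = 0.05 with the table's sizes and 6 degrees of freedom, power is about 80% for 0.1 and over 99% for 0.2.
- If *s* is only 0.005 or 0.01, the plain regression's type I error is about 6% or 8%.
- The 25% seasonal variation concerns mortality, and a minimum of two measurements a day for everyone may damp any seasonal effect on frequency.
- The worst allocations in step 3 are extremes. The averages are the fairer summary.
- The missing period term affects the mortality and length-of-stay models too.

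**Conclusion.** The concern holds. Followed as written, the SAP allows an analysis of a co-primary endpoint that ignores the clustering and the cross-over structure of its own design. The 0.04 is arithmetically correct for independent patients; the fault is that it states no allowance for clustering.

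The plain regression stays near 5% only if hospital-by-period variation and the period shift are both negligible and each hospital's volumes are balanced across periods. The SAP neither states nor justifies these conditions. An assumed *s* of 0.02, under 1% of the mean of 2.3, already gives a type I error of 16–18% and, with the small-sample reference, cuts power for 0.04 to 60–64%. All such figures are conditional on the assumed SDs and shifts. They show how sensitive the result is and do not predict what the trial will find.

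**What to change.** State in Primary outcome analysis that scores per patient per day are analysed with hospital and period effects, age and sex, and a standard error that allows for hospital-by-period variation with a small-sample correction. A hospital-by-period random effect or a cluster-period summary analysis would do. In Sample size calculation, restate 0.04 over a stated range of hospital-by-period SD using the same small-sample reference, or label it as ignoring clustering.

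The cost is one or two sentences and some analysis code, with no extra patients. The price is wider confidence intervals and a less favourable detectable difference. The choice of method also matters. In simulation, an unweighted cluster-period t test holds its level (4.5–4.9%) but has only 79% power for 0.04 even at *s* = 0. Weighting by size recovers 89%, but its type I error reaches 6–7% once hospital-by-period variation is present. The SAP should name the version chosen before outcome data are available.

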The trial was presented to the Regional Ethics Committee, who decided that no formal approval was needed in accordance with Danish law (J.nr. 1701733). The Danish Data protection agency has approved the project. The trial will be registered at clinicaltrials.gov.

Existing workflows are utilized as well as I-EWS is built into SP, so we do not expect the personal to experience a higher workload. When the possibility to individually adjust the observational frequency is given, there is a risk of overlooking critical illness. Therefore, the study only allows a reduction of maximum four points. When carried out, this means that a high EWS score will still trigger more frequent observation. The overall ethical assessment is that the study is safe. As

observed in previous research (publication under review) the introduction of clinical assessment when using triage have improved the risk evaluation in emergency patients, therefore we do not expect that the study will bring along a higher risk for the hospitalized patient.

Statistical analysis plan

Sep 18, 2018, (revised July 11, 2019)

This document contains the statistical analysis plan for the I-EWS study. The statistical analysis plan has been completed prior to the availability of the outcome data and aims to clarify the analyses.

Time line

The study will start at October 1, 2018. Due to implementation patients will be enrolled at October 15, 2018 with planned end of inclusion after one year, October 1, 2019. Follow-up will be concluded on November 1, 2019. The primary analysis will be conducted when the last patient has been followed for 30 days and data is available, which is expected to be Jan 2020.

Background

The primary research question is: A New EWS algorithm (I-EWS) that systematically incorporate clinical assessment, allowing nurses to adjust the I-EWS score will be non-inferior to the existing EWS algorithm and lead to fewer unnecessary EWS measurements, allowing a better utilisation of limited resources.

The study is a cluster-randomized cross-over multi-centre controlled interventional trial conducted at eight large hospitals.

Inclusion/Exclusion criteria

Eligible hospitals

- 1. Located in the Capital Region or Region Zealand I Denmark
- 2. Arrival of acutely admitted patients in on-site Emergency department
- 3. Systemised use of Early Earning Score (EWS) on patients admitted
- 4. Access to Medical Emergency Team
- 5. Access to Intensive Care Units (ICU)

Patient inclusion criteria

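### The planned mortality effect by hospital compares winter with summer within each hospital, and no period term is specified, so its interaction test can be significant from season alone

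*SAP*

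**What the plan says.** Under Definition of clusters: "Each hospital will generate one cluster and two (time) periods (control and intervention"). Under Randomisation, one date applies to all hospitals: "A cross-over will occur after 6.5 months and is expected to be at April 15, 2019". Under Time line: "Due to implementation patients will be enrolled at October 15, 2018 with planned end of inclusion after one year, October 1, 2019". Under Primary outcome analysis: "Each period will start with 14 days of implementation, and before cross-over patients will be followed by an observation period of 30 days", and patients admitted in those windows are left out.

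The mortality model is a logistic regression that allows for clustering and adjusts for hospital ID, age and sex. Neither the main nor the subgroup analysis has a term for period, season or calendar time.

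Subgroup analyses of primary endpoint then plans both primary outcomes by subgroup, with interaction tests and a forest plot. One subgroup is the hospital: "admissions at defined cluster, and according to the primary discharge diagnosis".

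The Sample size calculation itself assumes "a variation in mortality of 25% over the course of the year".

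**The concern.** In a two-period cluster cross-over, season cancels from the pooled effect because some hospitals use the intervention in winter and others in summer. A single hospital has no opposite sequence to cancel against. Its I-EWS versus EWS contrast is its winter-summer contrast, with the sign set by the sequence it drew.

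The forest plot could therefore show apparent harm in hospitals that had I-EWS in winter and apparent benefit in those that had it in summer, backed by a significant interaction test, when only the calendar differs. In a non-inferiority trial on mortality, readers may take such a plot as evidence about safety at particular hospitals.

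**Working it through.** **1. The plan's own figure.** Inputs from the Sample size calculation: 150,000 patients (75,000 per arm assumed), mortality 2.9%, margin 0.5 points, true effect 0. SE = √(2 × 0.029 × 0.971 / 75,000) = 0.000867. Power = Φ(0.005/0.000867 − 1.96) = Φ(3.81) = 0.9999, ignoring clustering and season. This agrees with the stated power above 90%, which is not in dispute.

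**2. Analysed windows.** Period 1 runs from 15 October 2018 to 15 March 2019, since the 30 days before 15 April are dropped (152 days). Period 2 runs from 29 April, since 14 days after cross-over are dropped, to 30 September 2019 (155 days).

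**3. What can be identified.** Let τ_h be hospital h's true log odds ratio and π the common log odds ratio of period 1 to period 2.

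- I-EWS first: the observed contrast estimates τ_h + π.
- EWS first: the observed contrast estimates τ_h − π.

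There are 16 hospital-period cells. Hospital (8 columns) plus hospital-specific treatment (8) already saturates them. Adding period gives 17 columns of rank 16. Differences between hospitals in the same sequence are free of π, which gives 8 − 2 = 6 df. The seventh, the contrast between the two sequences, contains 2π and cannot be separated from season.

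**4. Size of the season.** The SAP does not say whether 25% is peak-to-trough or plus or minus, nor when the peak falls. Assumption: mortality = 2.9% × [1 + a·cos(2π(day − peak)/365.25)], with the peak between 15 January and 4 February. For a 15 January peak the cosine averages 0.707 over period 1 and −0.729 over period 2.

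| Reading of 25% | a | Period 1 v period 2 (15 Jan peak) | Gap, points | Odds ratio by peak date (4 Feb to 15 Jan) |
|---|---|---|---|---|
| Half the peak-to-trough size | 0.0625 | 3.03% v 2.77% | 0.26 | 1.09 to 1.10 |
| Peak-to-trough | 0.125 | 3.16% v 2.64% | 0.52 | 1.18 to 1.20 |
| Plus or minus | 0.25 | 3.41% v 2.37% | 1.04 | 1.40 to 1.46 |

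With no treatment effect, hospitals with I-EWS in winter show the odds ratio in the last column and the others show its inverse. On the peak-to-trough reading that is 1.18 to 1.20 or 0.83 to 0.85. The absolute gap of 0.46 to 0.52 points is about the size of the margin.

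**5. False rejection by the 7-df test without a period term.** Hospital sizes and deaths come from the table at the end of the SAP, scaled to 150,000 and split equally between periods. Each hospital's weight w_h is the inverse variance of its log odds ratio, and θ_h = ±π. The noncentrality is λ = Σ w_h(θ_h − θ̄)², and the critical value is 14.07. On the peak-to-trough reading with a 15 January peak, Σw_h ≈ 1,062 and π = ln 1.204 = 0.186, so λ can reach about 1,062 × 0.0345 ≈ 36.6. Over all 36 allocations with two large and two small hospitals per sequence, and over the range of peak dates:

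- half size: rejection 0.44 to 0.57
- peak-to-trough: 0.988 to 0.998
- plus or minus 25%: essentially 1.00

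**6. Simulation check** (10,000 runs, one allocation, 15 January peak, no treatment effect). The 7-df test without period rejected in 4.8% of runs with no season, 56.4% at odds ratio 1.10, 99.8% at 1.20 and 100% at 1.46. The 6-df within-sequence test rejected in 4.5% to 5.2% throughout.

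**7. Pooled effect.** On the peak-to-trough reading, season moves the pooled odds ratio only to between 0.97 and 1.03, depending on allocation.

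**The case against.** Five points can be made for the plan.

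- *Only one of seven degrees of freedom is lost.* This stands. A reader might infer that heterogeneity between hospitals cannot be studied at all, but steps 3 and 6 show otherwise: with a period term and a season common to all hospitals, six contrasts can be tested at the right error rate. The SAP specifies neither the term nor the restriction, and hospital-specific effects stay unidentified either way.
- *The false-positive rate rests on assumptions.* This also stands. The SAP gives a bare 25%, and the curve and peak date are assumed here. The calculation leaves out age and sex adjustment and treats patients as independent, whereas the SAP's model allows for clustering. A significant test is therefore not certain. Yet a season of half the size still gives about nine times the nominal 5% or more.
- *The evidence concerns mortality only.* Correct. Treatment is aliased with period for scores per patient per day as well, but the SAP gives no seasonal figure for them, so no size is claimed.
- *The SAP also says* "Assessment of cluster-level differences will be performed". A reader might take this as a second plan for hospital-specific treatment effects. It follows the sentence on the intraclass correlation and may mean only outcome differences between hospitals, which the design can show. The point does not rely on it.
- *It is one subgroup, and no decision rule depends on it.* True, and this limits the consequence. The output is nevertheless prespecified, tested and plotted without a caveat.

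**Conclusion.** The point holds for mortality. The aliasing of treatment with period inside each hospital is exact and needs no assumption about season. The size does need one: with a cosine season peaking in January to early February and no true effect, false rejection is about 99% if 25% is peak-to-trough, about 45 to 57% at half that size, and essentially 100% if plus or minus 25%. Hospital-specific effects and the between-sequence contrast cannot be recovered by a common period term. The other six contrasts can, if season acts equally in all hospitals.

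A reader might go further and infer that the primary comparison is invalid. The documents do not support that: the two sequences largely balance season, and the pooled odds ratio stays within 0.97 to 1.03 on the peak-to-trough reading. This should be changed before analysis, but it does not overturn the main result.

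**What to change.** For mortality, remove hospital-specific treatment effects from the interaction-tested subgroups and the forest plot. Show instead a descriptive table or figure of mortality per hospital and period, ordered by sequence and labelled with season, stating that a single hospital's contrast is not a treatment effect.

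If a test of heterogeneity between hospitals is wanted, add a period term, restrict the test to the 6-df within-sequence contrasts, and state the assumption that season acts equally in all hospitals.

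A subgroup by the randomisation stratum (above or below 25,000 admissions) is optional and answers a different question. The table has four large and four small hospitals, so treatment by stratum is estimable with a stratum-specific period effect if each stratum splits two and two. The SAP states stratified 1:1 randomisation without describing blocking, so that split should be confirmed first.

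The cost is SAP wording and one model term. Hospital-specific effect estimates are given up, which the design cannot provide in any case, and one interaction degree of freedom is lost.
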